12.5 Accrual Estimates

We estimate that approximately 2 patients with head and neck cancer start radiation therapy in a given week in our department. Assuming that 2/3 of these patients would be eligible for this study and would provide consent with a 10% attrition rate, we estimate that this study will complete accrual of 170 patients in 142 weeks (or 36 months).

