APPENDIX A: PARTICIPANT ELIGIBILITY CHECKLIST	
APPENDIX B: STANFORD RADIATION DERMATITIS SCORING SYSTEM	
APPENDIX C: CTCAE Verson 4.03 For Radiation Dermatitis	
APPENDIX D: MODIFIED BRIEF PAIN INVENTORY	

PROTOCOL SYNOPSIS

TITLE	Randomized Study of Topical Dilute Hypochlorite for the		
	Prevention of Radiation Dermatitis in Head and Neck Cancer		
STUDY PHASE	Phase III		
STUDY REAGENT	1:1000 dilute hypochlorite solution (0.005%) administered to the skin prior to daily radiation therapy		
PRIMARY OBJECTIVE(S)	The primary objective is to determine whether prophylactic topical dilute HOCl reduces the proportion of patients who develop Grade E radiation dermatitis as scored on the Stanford Radiation Dermatitis Scoring System (SRDSS)		
SECONDARY OBJECTIVE(S)	 Secondary objectives are: To determine whether this agent delays the time to development of Grade E radiation dermatitis To determine whether this agent improves quality-of-life and pain scores associated with radiation dermatitis 		
TREATMENT SUMMARY	Eligible patients will be randomized to daily application of topical dilute hypochlorite versus placebo for 10 minutes within 3 hours prior to daily radiation treatment. When patients in either arm develop Grade E radiation dermatitis during the radiotherapy course, they will be switched to topical dilute hypochlorite treatment daily per standard of care. Patients will complete the Modified Brief Pain Inventory at study entry, at 40-50 Gy through the radiation treatment course, at the end of radiation treatment, and at the follow-up visit 3-12 weeks after radiation treatment.		
SAMPLE SIZE	170 Patients (85 patients per arm)		
STATISTICAL CONSIDERATIONS	Sample Size Calculation: From prior clinical experience, we anticipate that 80% of patients will experience Grade E radiation dermatitis with standard skin care. In order to detect a 20% reduction in patients with Grade E dermatitis (80% vs 60% in those treated with dilute hypochlorite solution) with a two-sided alpha of 0.05 and beta of 80%, 170 patients will be enrolled. Primary endpoint: The proportion of patients in each arm who develop Grade E radiation dermatitis (as defined by the Stanford Radiation Dermatitis Scoring System) during a course of		

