4. TREATMENT PLAN

4.1 Description of Treatment Plan

Patients will be screened for study eligibility by the research team when they arrive for their initial consultation for radiotherapy. If eligible and willing to participate, patients will sign informed consent and be enrolled in the study.

Baseline

Patients will undergo a clinical skin assessment by the treating physician. Patients will also complete the MBPI, and photographs will be taken of the neck to represent their baseline skin. Patients will be stratified by type of chemotherapy and randomized.

During Radiation Therapy

Prior to each radiation treatment, the study agent or placebo (depending on randomization arm) will be applied to the area of the skin to be irradiated for 10 minutes within 3 hours of the patient's daily scheduled radiotherapy treatment. A nurse or qualified research member will instruct the patient on its application on the day of trial consent. After this initial instruction, the patient will self-apply the solution to their skin prior to treatment when he/she arrives to the radiation treatment area. There are clinic rooms that the patient can utilize to self-apply the solution prior to their daily radiation treatment. A nurse or qualified research member will check in with the patient once per week and

answer any questions if applicable. Patients will be instructed to use Vaseline as a moisturizer during the radiation treatment course per standard of care.

A clinical skin assessment by the treating physician will be performed once weekly during the radiation treatment course and at the end of radiation treatment +/- 10 days. At each clinical skin assessment, skin toxicity will be graded using the Stanford Radiation Dermatitis Scoring System and the CTCAE Scoring System. Photographs will also be taken at 40-50 Gy of radiation treatment and at the end of radiation treatment +/- 10 days.

Patients will also complete the Modified Brief Pain Inventory at the time of randomization, at 40-50 Gy of radiation treatment, at the end of radiation treatment +/- 10 days, and at the follow-up visit 3-12 weeks after the completion of the radiation treatment course.

Follow Up

During the patient's follow up appointment 3-12 weeks after completion of the radiation treatment course, the patient will complete the MBPI, a clinical skin assessment will be performed, and photographs will be taken of their treatment area.

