12.2 Sample Size Justification

The primary endpoint is the proportion of patients who develop Grade E radiation dermatitis (as defined by the Stanford Radiation Dermatitis Scoring System) in each arm during a course of radiation therapy. From prior clinical experience, we anticipate that 80% of patients will experience Grade E radiation dermatitis with standard skin care. In order to detect a 20% reduction in patients with Grade E radiation dermatitis (80% vs 60% in those treated with dilute hypochlorite solution) with Type I error of 0.05 and Type II error of 20% (power of 80%), 170 patients will be enrolled.

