APPENDIX A: Participant Eligibility Checklist

A Participant Eligibility Checklist must be completed in its entirety for each subject prior to registration. The completed, signed, and dated checklist must be retained in the patient's study file and the study's Regulatory Binder.

The study coordinator, treating physician and an independent reviewer must verify that the participant's eligibility is accurate, complete, and legible in source records. A description of the eligibility verification process should be included in the EPIC or other Electronic Medical Record progress note.

Protocol Title:	
Protocol Number:	
Principal Investigator:	[name]

II. Subject Information:

Subject Name/ID:		
Gender: Male	Female	

III. Study Information:

SRC Approved	IRB Approved	Contract signed
		

IV. Inclusion/Exclusion Criteria

Inclusion Criteria (From IRB approved protocol)		Yes	No	Supporting Documentation*
1.	Patients with head and neck cancer who plan to undergo radiation			
	therapy to the head and neck region			
2.	Patient must be at least 18 years of			
3.	Ability to understand and the willingness to sign a written			
	informed consent document			
Exclusion Criteria (From IRB approved protocol)				
1.	Prior radiation therapy to the head and neck region or prior chemotherapy for head and neck cancer (induction chemotherapy NOT excluded)			
2.	Maximum RX dose <45 Gy in the approved radiation treatment plan			
3.	Patients with scleroderma or discoid lupus			

*All subject files must include supporting documentation to confirm subject eligibility. The method of confirmation can include, but is not limited to, laboratory test results, radiology test results, subject self-report, and medical record review.

IV. Statement of Eligibility

By signing this form of this trial I verify that this subject is [eligible / ineligible] for participation in the study. This study is approved by the Stanford Cancer Institute Scientific Review Committee, the Stanford IRB, and has finalized financial and contractual agreements as required by Stanford School of Medicine's Research Management Group.

Physician Signature:	Date:
Printed Name:	

Secondary Reviewer Signature:	Date:
Printed Name:	

Study Coordinator Signature:	Date:
Printed Name:	

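### Does the target of 170 patients mix two bases, before and after 10% attrition, and so lose its 80% power?

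*Combined protocol and SAP*

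**What the plan says.** Section 12.2 sizes the trial to detect Grade E dermatitis in 80% versus 60% of patients: "with Type I error of 0.05 and Type II error of 20% (power of 80%), 170 patients will be enrolled". The Protocol Synopsis gives "170 Patients (85 patients per arm" and, for the error rates, "with a two-sided alpha of 0.05 and beta of 80%, 170 patients will be enrolled". Neither place mentions attrition.

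Section 12.5 takes about 2 patients a week starting radiotherapy. It then sets out how many of them will count: "Assuming that 2/3 of these patients would be eligible for this study and would provide consent with a 10% attrition rate". The duration that results is given in the same sentence: "we estimate that this study will complete accrual of 170 patients in 142 weeks (or 36 months".

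Two places bear on what enrolled means. Section 4.1 says: "If eligible and willing to participate, patients will sign informed consent and be enrolled in the study". Appendix A says: "A Participant Eligibility Checklist must be completed in its entirety for each subject prior to registration". One exclusion on that checklist is "Maximum RX dose <45 Gy in the approved radiation treatment plan", which can be confirmed only once the radiation plan exists.

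**The concern.** The same number seems to do two jobs. In Section 12.5 it is what remains after a tenth of consenting patients have dropped away. In Section 12.2 it is the number enrolled, and Section 4.1 puts enrolment at consent. Read literally, recruitment could stop at 170 consents or at about 189. If it stopped at 170 and the tenth lost had no primary outcome, the analysis would rest on about 153 patients and power would be below the 80% claimed.

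Two misprints add to the impression that the design figures were not checked against each other: the conversion of 142 weeks to 36 months, and a beta of 80% in the synopsis.

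**Working it through.** **Accrual (inputs from Section 12.5: 2 per week, 2/3 eligible and consenting, 10% attrition, target 170).**

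- Consenting: 2 × 2/3 = 1.333 per week. After attrition: 1.333 × 0.9 = 1.2 per week.
- 170/1.2 = 141.7 weeks, which reproduces the printed 142.
- Without attrition: 170/1.333 = 127.5 weeks, which does not.

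So Section 12.5 counts 170 net of attrition. The implied number of consents is 170/0.9 = 188.9, about 189.

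**Months.** At 4.348 weeks per calendar month, 142 weeks is 32.7 months, and 36 months would be 156.5 weeks. Four-week months give 142/4 = 35.5, the likely source of 36.

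**Sample size (inputs from Section 12.2 and the synopsis: 0.8 versus 0.6, two-sided 0.05, power 80%).** On the log odds ratio scale, which suits the logistic regression of Section 12.3:

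- ln[(0.8/0.2)/(0.6/0.4)] = ln 2.667 = 0.981
- 1/(0.8 × 0.2) + 1/(0.6 × 0.4) = 6.25 + 4.17 = 10.42
- n per arm = (1.960 + 0.842)² × 10.42/0.981² = 84.99, so 85 per arm and 170 in all.

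This gives the plan's figure exactly. The pooled formula for a difference in proportions gives 82 per arm (164). Hence 170 is enough as the number with outcomes and carries little or no allowance for loss, depending on the formula. A beta of 80% taken literally would mean 20% power and about 14 per arm, so the synopsis wording is plainly a slip for power.

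**Power under each reading (unadjusted).**

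| Patients with outcome | Formula (log odds ratio, pooled, unpooled) | Exact, Wald logistic | Exact, chi-square |
|---|---|---|---|
| 170 (85/85) | 80.0%, 81.8%, 83.0% | 82.0% | 82.2% |
| 164 (82/82) | – | 80.7% | 80.7% |
| 162 (81/81) | – | 80.1% | 80.2% |
| 153 (77/76, 76/77) | 75.7%, 77.6%, 79.0% (at 76.5 per arm) | 77.9%, 77.6% | 78.5%, 77.8% |

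Splits are control/experimental. By exact enumeration, 170 absorbs 6 missing outcomes (Wald) or 8 (chi-square) under any near-equal split. Power is below 80% under every near-equal split from 9 or 11 missing respectively. All of these are fewer than the 17 implied by 10% of 170.

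**With the planned adjustment for chemotherapy type.** The documents give no Grade E rate or patient mix by chemotherapy type, so these simulations rest on assumptions: three cisplatin/cetuximab/none mixes (50/15/35, 40/10/50, 34/33/33), marginal rates held at 80% and 60%, and 40,000 trials per case. At 153 patients, power is 78.0% to 78.1% if chemotherapy type is not prognostic, 78.8% to 79.8% if moderately so, and 81.3% to 84.1% if strongly so.

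**Reading the sections together.** Arms exist only after randomisation, so 85 per arm in the synopsis counts randomised patients. Under Sections 2.3 and 4.1 randomisation follows consent, and Section 2.3 allows two weeks for planning. Exclusion 3.2.2 depends on the approved plan, and Appendix A requires the checklist before registration. A patient can therefore consent and never be randomised. If the 10% is lost at that stage, Sections 12.2 and 12.5 and the synopsis all describe 170 randomised from about 189 consents over 142 weeks.

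**The case for a change.** The strongest case for a change is that no section says when the 10% is lost. Section 4.1 equates enrolment with consent. Section 3.1.3 allows consent up to 3 days after radiotherapy starts, which leaves little time for loss before randomisation in those patients. The two-thirds in Section 12.5 already covers eligibility, so plan-based exclusions may not account for the 10%. Even if 170 are randomised, Section 12.2 makes no allowance for later loss. A correction would cost only a few words.

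Much of this stands as description: the timing of attrition is unstated, and both misprints are certain. It does not establish a conflict. Section 4.1 is a one-sentence summary of procedure and does not define the sample-size base, while 85 per arm does point to randomisation. Nor does attrition equal a missing outcome. Section 10.1 has patients examined weekly as standard care, Section 10.3.1 has the treating physician grade the skin weekly, and Section 4.3 lets patients removed from the study continue clinical assessment. Writing 153 patients and 78% power into the plan would turn a worst case that the documents never state into a design assumption.

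**Conclusion.** No change follows. Section 12.5 itself counts 170 net of attrition, and the synopsis's arm sizes fit 170 randomised. On that reading the stated 80% power is delivered: 80.0% to 83.0% by formula and about 82% exactly, provided nearly all randomised patients have a grade.

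The shortfall needs two unstated conditions together: recruitment stopping at 170 consents, and about half or more of the implied 17 lost patients lacking the primary outcome. If all 17 lack it, with near-equal loss in the two arms, exact unadjusted power is 1.5 to 2.4 points below 80%. The planned adjustment could remove that shortfall if chemotherapy type is strongly prognostic, though this rests on assumed mixes and rates.

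The timing of attrition is a missing detail that the trial team can settle sensibly from the arm sizes and the accrual sum. The other two items are clerical. Section 12.2 already gives the correct error rates, and recruitment ends on a patient count rather than a number of months. Neither slip touches the sample size, the analysis, a stopping rule or the conclusion.

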12.6 Inter-Rater Reliability Testing

Inter-rater reliability will be evaluated using the kappa statistic. A kappa statistic of 0.8 will define good inter-rater reliability. For details of how this method will be implemented, see Section 10.2.

12.7 Criteria for Future Studies

If our hypothesis is correct and the hypochlorite solution reduces the incidence of Grade E radiation dermatitis, we plan to initiate a multi-institution, phase III randomized clinical trial with the intention of establishing the prophylactic use of topical dilute hypochlorite solution as standard of care to prevent radiation dermatitis in patients undergoing radiation therapy for head and neck cancer.

APPENDIX A: Participant Eligibility Checklist

A Participant Eligibility Checklist must be completed in its entirety for each subject prior to registration. The completed, signed, and dated checklist must be retained in the patient's study file and the study's Regulatory Binder.

The study coordinator, treating physician and an independent reviewer must verify that the participant's eligibility is accurate, complete, and legible in source records. A description of the eligibility verification process should be included in the EPIC or other Electronic Medical Record progress note.

Protocol Title:	
Protocol Number:	
Principal Investigator:	[name]

II. Subject Information:

Subject Name/ID:		
Gender: Male	Female	

III. Study Information:

SRC Approved	IRB Approved	Contract signed
		

IV. Inclusion/Exclusion Criteria

Inclusion Criteria (From IRB approved protocol)		Yes	No	Supporting Documentation*
1.	Patients with head and neck cancer who plan to undergo radiation			
	therapy to the head and neck region			
2.	Patient must be at least 18 years of			
3.	Ability to understand and the willingness to sign a written			
	informed consent document			
Exclusion Criteria (From IRB approved protocol)				
1.	Prior radiation therapy to the head and neck region or prior chemotherapy for head and neck cancer (induction chemotherapy NOT excluded)			
2.	Maximum RX dose <45 Gy in the approved radiation treatment plan			
3.	Patients with scleroderma or discoid lupus			

*All subject files must include supporting documentation to confirm subject eligibility. The method of confirmation can include, but is not limited to, laboratory test results, radiology test results, subject self-report, and medical record review.

IV. Statement of Eligibility

By signing this form of this trial I verify that this subject is [eligible / ineligible] for participation in the study. This study is approved by the Stanford Cancer Institute Scientific Review Committee, the Stanford IRB, and has finalized financial and contractual agreements as required by Stanford School of Medicine's Research Management Group.

Physician Signature:	Date:
Printed Name:	

Secondary Reviewer Signature:	Date:
Printed Name:	

Study Coordinator Signature:	Date:
Printed Name:	

APPENDIX B: Stanford Radiation Dermatitis Scoring System

Grade	Clinical finding
Α	No skin change
В	Faint, barely detectable erythema
С	Follicular rash, hyperpigmentation, evolving erythema
D	Dry desquamation, brisk erythema
Ε	Moist desquamation
F	Bleeding, ulceration, and/or infection

APPENDIX C: CTCAE Version 4.03

Grade	Clinical finding
0	No skin change
1	Faint erythema or dry desquamation
2	Moderate to brisk erythema; patchy moist desquamation, mostly confined to skin folds and creases; moderate edema
3	Moist desquamation in areas other than skin folds and creases; bleeding induced by minor trauma or abrasion
4	Life-threatening consequences; skin necrosis or ulceration of full-thickness dermis; spontaneous bleeding from involved site; skin graft indicated
5	Death

APPENDIX C: Modified Brief Pain Inventory

Please fill in the following: First Name (1) Last Name (2)

Time point for survey:

- **O** Baseline prior to radiation treatment (1)
- \bigcirc 40-50 Gy of radiation treatment (2)
- **O** Last day of radiation treatment (3)
- Follow-up visit 3-12 weeks after radiation treatment course (4)

Q1 Please rate your current level of skin discomfort.

- **O** 0 (0)
- **O** 1(1)
- **O** 2(2)
- **O** 3(3)
- $O_{4}(4)$
- **O** 5(5)
- **O** 6(6)
- **O** 7 (7)
- **O** 8 (8)
- O 9(9)
- **O** 10 (10)

Q2 Please rate your pain by selecting the one number that best describes your pain at its worst in the last 24 hours.

- **O** 0 (0)
- **O** 1(1)
- **O** 2 (2)
- **O** 3 (3)
- **O** 4 (4)
- **O** 5 (5)
- **O** 6 (6)
- **O** 7 (7)
- **O** 8 (8)
- O 9(9)
- **O** 10 (10)

Q3 Please rate your pain by selecting the one number that best describes your pain at its least in the last

24 hours.

- **O** 0 (0)
- **O** 1 (1)
- **O** 2 (2)
- **O** 3 (3) **O** 4 (4)
- O = 4 (4)O = 5 (5)
- O 6(6)
- **O** 7 (7)
- O = 8 (8)
- O 9(9)
- O 10(10)

Q4 Please rate your pain by selecting the one number that best describes your pain on the average.

- (0) 0 **C**
- **O** 1 (1)
- **O** 2 (2)
- **O** 3 (3)
- **O** 4 (4)
- **O** 5 (5)
- **O** 6(6)
- **O** 7(7)
- **O** 8 (8)
- **O** 9 (9)
- **O** 10 (10)

Q5 Please rate your pain by selecting the one number that tells how much pain you have right now.

- **O** 0 (0)
- **O** 1(1)
- **O** 2 (2)
- **O** 3 (3)
- **O** 4 (4)
- **O** 5 (5)
- **O** 6 (6)
- **O** 7 (7)
- **O** 8 (8) **O** 9 (9)
- O 10(10)

Q6 What treatments or medication are you receiving for your pain?

Q7 In the last 24 hours, how much relief have pain treatments or medications provided? Please select

the one percentage that most shows how much relief you have received?

- \bigcirc 0% (No Relief) (0)
- **O** 10% (1)
- **O** 20% (2)
- **O** 30% (3)
- **O** 40% (4)
- **O** 50% (5)
- **O** 60% (6)
- **O** 70% (7)
- **O** 80% (8)
- **O** 90% (9)
- \bigcirc 100% (Complete Relief) (10)

Select the one number that describes how, during the past 24 hours, pain has interfered with your:

Q8 General Activity

- **O** 0 (0)
- **O** 1(1)
- **O** 2 (2)
- **O** 3 (3)
- **O** 4 (4)
- **O** 5 (5)
- **O** 6(6)
- **O** 7(7)
- **O** 8 (8)
- **O** 9(9)
- **O** 10 (10)

Q9 Mood

- **O** 0 (0)
- **O** 1(1)
- **O** 2 (2)
- **O** 3 (3)
- **O** 4 (4)
- **O** 5 (5)
- **O** 6 (6)
- **O** 7 (7)
- **O** 8 (8)
- O 9(9)
- **O** 10 (10)

Q10 Walking Ability

- **O** 0 (0)
- **O** 1(1)
- **O** 2 (2)
- **O** 3 (3)
- **O** 4 (4)
- **O** 5 (5)
- **O** 6 (6)
- **O** 7 (7)
- **O** 8 (8)
- **O** 9 (9)
- **O** 10 (10)

Q11 Normal Work (includes both work outside the home and housework)

- **O** 0 (0)
- **O** 1 (1)
- **O** 2 (2)
- **O** 3 (3)
- **O** 4 (4)
- **O** 5 (5)
- **O** 6(6)
- **O** 7(7)
- **O** 8 (8)
- **O** 9 (9)
- **O** 10 (10)

Q12 Relations with other people

- **O** 0 (0)
- **O** 1(1)
- **O** 2 (2)
- **O** 3 (3)
- **O** 4 (4)
- **O** 5 (5)
- **O** 6(6)
- **O** 7 (7)
- **O** 8 (8)
- **O** 9 (9)
- **O** 10 (10)

Q13 Sleep

- **O** 0 (0)
- **O** 1 (1)
- $O_{2}(2)$
- **O** 3 (3) **O** 4 (4)
- O = 4 (4)O = 5 (5)
- O 6(6)
- **O** 0 (0) **O** 7 (7)
- O = 7(7)O = 8(8)
- O = 0 (8)O = 9 (9)
- O 10(10)

Q14 Enjoyment of Life

- **O** 0 (0)
- **O** 1 (1)
- **O** 2 (2)
- **O** 3 (3)
- **O** 4 (4)
- **O** 5 (5)
- **O** 6(6)
- **O** 7(7)
- **O** 8 (8)
- **O** 9 (9)
- **O** 10 (10)

Q15 At this point, how much do you feel that this skin treatment will improve or prevent your skin discomfort during radiation treatment? (Asked only at baseline)

- **O** 0% (No Relief) (0)
- **O** 10%(1)
- **O** 20% (2)
- **O** 30% (3)
- **O** 40% (4)
- **O** 50% (5)
- **O** 60% (6)
- **O** 70% (7)
- **O** 80% (8)
- **O** 90% (9)
- \bigcirc 100% (Complete Relief) (10)

Copyright 1991 [name] Pain Research Group All Rights Reserved
